### 4.2 Scientific rationale for study design

In healthy volunteers without hepatic impairment, the concentration-time profiles of both PSL and [REDACTED] demonstrated a biphasic disposition with a terminal elimination half-life ( $t_{1/2}$ ) of approximately 6 hours for the parent, and 10 to 14 hours for the metabolite, which were independent of dose. However, steady state was achieved after 2 to 3 days of treatment for both moieties, and the accumulation ratio for the parent was approximately 1.7 (range 1.59 to 2.11), which was greater than predicted by the single dose PK (N01386).

As PSL is cleared hepatically, exposure to drug in hepatically impaired participants could increase primarily due to a reduction in PSL clearance, among other factors. This can be illustrated by an increase in  $t_{1/2}$ , a prolonged washout time, and an increased time to reach steady state with multiple dosing. To facilitate the design of this study, a doubling of  $t_{1/2}$  and time to steady state has been assumed in hepatically impaired participants. Therefore, the Washout Period required to capture the  $t_{1/2}$  of the [REDACTED] has been calculated to be 5 to 6 days (assumes a  $t_{1/2}$  of 28 hours) and the time to steady state has been calculated to be 4 to 6 days.

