- i Pharmacokinetic blood samples will be taken at the following time points: Predose and 15 minutes, 30 minutes, 45 minutes, 1h, 1.5h, 3h, 4h, 5h, 6h, 8h, 12h, 24h (Day 2), 48h (Day 3), 72h (Day 4), and 96h (Day 5) postdose. On Days 8, 9, 10, and 11, PK samples will be taken at predose. On Day 12, PK blood samples will be taken at the following time points: predose and 15 minutes, 30 minutes, 45 minutes, 1h, 1.5h, 3h, 4h, 5h, 6h, 8h, 12h, 24h (Day 13), 48h (Day 14), 72h (Day 15), and 96h (Day 16) postdose.
- j Two blood samples will be collected after multiple doses at steady state (Day 12 predose and 1.5h postdose [ $\sim t_{max}$ ]) for PPB.
- k Urine for PK assessment will be collected from all study participants on Day 1 at predose and from 0h to <12h and 12h to <24h, on Day 2 from 24h to <48h, on Day 3 from 48h to <72h, on Day 4 from 72h to <96h, (before the 8am cutoff on Day 5) postdose. Urine for PK assessment will also be collected from all study participants on Day 12 from 0h to <12h postdose.

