### **5.3 Lifestyle restrictions**

#### **5.3.1 Meals and dietary restrictions**

- Participants will complete a light meal 30 minutes prior to each morning dose of PSL and will complete a standard meal 30 minutes prior to the evening dose. The standardized meal composition and timing should be consistent for all days the participant is on study. On days when PK assessments will be taken, study participants will complete a standardized meal (same macronutrient will be administered for minimizing covariates) in the afternoon and evening.
- Padsevonil will be administered orally with 8oz (240mL) water. Between 1h predose and 2h postdose, the total intake of beverages should be limited to 100mL.
- The participant must not ingest grapefruit, starfruit, and pawpaw (as beverage, fruit, or supplements) within 72h before the study medication administration. These fruits are not allowed during the Treatment Period and throughout the study.

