10.4	Vital signs, physical findings, and other observations related to safety	32
10.4.1	Vital signs	32
10.4.2	Electrocardiograms	32
10.4.3	Other safety variables	33
10.4.3.1	Physical examination	33
10.4.3.2	Columbia-Suicide Severity Rating Scale	34
11	OTHER ANALYSES	34
12	REFERENCES	35
13	APPENDICES	36

This document cannot be used to support any marketing authorization application and any extensions or variations thereof.
 REDACTED COPY

LIST OF ABBREVIATIONS

AE(s)	adverse event(s)
Ae	Cumulative amount of PSL or its metabolite excreted in urine (Amount excreted)
ALT	alanine aminotransferase
ALQ	above the limit of quantification
ANOVA	analysis of variance
AST	aspartate aminotransferase
AUC	area under the curve from time 0 to infinity
AUC _{0-t}	area under the curve from time 0 to the last quantifiable concentration
AUC ₀₋₁₂	area under the curve from time 0 to 12h after a single PSL dose
AUC _τ	area under the curve over a dosing interval
BID	twice daily
BLQ	below the limit of quantification
BMI	body mass index
CI	confidence interval
CL/F	apparent total clearance
CL _{SS} /F	apparent total clearance at steady-state
CL _R	Renal clearance of PSL
C _{max}	maximum observed plasma concentration
C _{max,ss}	maximum observed plasma concentration at steady-state
C _{trough}	Measured concentration at the end of a dosing interval at steady state
CRF	case report form
CRU	clinical research unit

CSR	clinical study report
CV	coefficient of variation
C-SSRS	Columbia-Suicide Severity Rating Scale
DEM	data evaluation meeting
ECG	electrocardiogram
EOS	End of Study
ETV	Early Termination Visit
EudraCT	European Union Drug Regulating Authorities Clinical Trials
FAS	Full Analysis Set
FDA	Food and Drug Administration
f_e	Fraction of the dose excreted unchanged
$f_{e_{met}}$	Fraction of the dose excreted as the metabolite
FU	Follow-up
geoCV	geometric coefficient of variation
ICF	Informed Consent form
ICH	International Council on Harmonisation
IMP	investigational medicinal product
IRN	International normalized ratio
IPD	important protocol deviation
LLOQ	lower limit of quantification
MedDRA	Medical Dictionary for Regulatory Activities
MD	Multiple dose
MR_{Ae}	Metabolic ratio for A_e
MR_{AUC}	Metabolic ratio for AUC
$MR_{AUC\tau}$	Metabolic ratio for $AUC\tau$

MR _{C_{max}}	Metabolic ratio for C _{max}
MR _{C_{max,ss}}	Metabolic ratio for C _{max,ss}
n	number of participants number of available observations
NCA	Noncompartmental analysis
PK Set	Pharmacokinetic Set

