3.2.2 Study periods

For each participant completing the study, the expected maximum duration of participation will be approximately 46 days with a maximum of 6 days exposure to investigational product, and will consist of the following periods:

- Screening/Baseline Period (Day -28 to Day -1)

The Screening Period consists of a single Screening Visit, which will be conducted at the unit within 28 days prior to check-in for treatment period, and a Baseline Visit, which will be conducted at the clinical research unit (CRU) 1 day prior to treatment period (on Day -1). Study participants will check-in at the CRU on Day -1.

- PSL Single Dose Administration Period (Day 1 to Day 7)

In the Single Dose Period, study participants will receive a single oral dose of 100mg PSL on Day 1, at approximately 8:00am, 30 minutes after a light meal has finished. No study drug will be administered on Days 2 to 7; assessments will be conducted during this time as specified in the Schedule of Activities (Table 2-). Days 2 to 7 are designated as a 6-day washout.

- PSL Multiple Dose Administration Period (Day 8 to Day 17)

In the Multiple Dose Period, study participants will receive multiple oral PSL doses on Days 8 to 12, followed by a 5-day washout (Days 13 to 17). Padsevonil will be administered BID, with one 100mg dose in the morning [approximately 8:00am] and one 100mg dose in the evening [approximately 8:00pm] on Days 8 to 11. One dose of 100mg of PSL will be administered on the morning of Day 12. The Follow-Up Period consists of an End of Study (EOS)/Early Termination Visit (ETV) performed after discharge on Day 18 or upon discontinuation of the study.

The end of the study is defined as the date of the last visit of the last participant in the study.

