9.1 Analysis of the primary pharmacokinetic variables

All deviations will be calculated relative to the last dose of study medication (on Day 1 for Single Dose Period and on Day 12 for Multiple Dose Period). Any samples that are obtained outside the tolerance window permitted at the specified time point will be discussed at the DEM and any possible exclusion from analysis will be documented accordingly. The primary PK variables in plasma used for PSL are: C_{max} , AUC_{0-t} and AUC for the Single Dose Period and $C_{max,ss}$ and AUC_{τ} for the Multiple Dose Period. C_{max} and $C_{max,ss}$ will be determined from the observed concentration and time data. AUC_{τ} , AUC and AUC_{0-t} will be computed using the linear up/log down trapezoidal rule.

The PK plasma concentrations and the primary PK parameters of PSL will be summarized by period, cohort, and nominal sampling times using descriptive statistics (number of available observations [n], arithmetic mean, median, standard deviation, minimum, maximum, geometric mean, geometric CV and 95% CI for the geometric mean [assuming log-normally distributed data]). Values below the LLOQ will be reported with a clear sign (flag variable in the dataset) indicating that they were below the LLOQ.

Individual participant concentration-time profiles of PSL will be displayed graphically in linear and semi-logarithmic scale. Combined individual (spaghetti) plots will be displayed by treatment period, cohort and analyte with all participants overlaid on the same plot (linear and semi-logarithmic scale).

Geometric mean profiles of plasma concentrations for PSL over time will be presented, with all cohorts overlaid on the same plot, in both linear and semi-logarithmic scale for each treatment period. For the linear scale plot only, the lower and upper 95% confidence interval (CI) for the geometric mean will be displayed.

All plasma concentration figures will include the LLOQ on the semi-logarithmic scale plots and will be based on scheduled times.

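### Does the plan need a rule for deciding whether the hepatically impaired cohort is at steady state on Day 12?

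*Protocol*

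**What the plan says.** Protocol 4.2 reports that healthy volunteers reached steady state in 2 to 3 days, for parent and metabolite alike. Terminal half-lives were about 6 h (parent) and 10 to 14 h (metabolite). For impaired participants it assumes that half-life and time to steady state both double, so that "the time to steady state has been calculated to be 4 to 6 days". It also reports parent accumulation of about 1.7 (range 1.59 to 2.11), "which was greater than predicted by the single dose PK".

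SAP 3.2.2 gives twice-daily doses at about 8:00am and 8:00pm on Days 8 to 11, and then: "One dose of 100mg of PSL will be administered on the morning of Day 12". The full profile follows that ninth dose.

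The steady-state label is attached to Day 12 throughout. Footnote j of the schedule in both documents reads "Two blood samples will be collected after multiple doses at steady state", and the SAP list of abbreviations defines Ctrough as "Measured concentration at the end of a dosing interval at steady state". Cmax,ss and CLss/F carry the same label.

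On sampling, footnote i of Protocol Table 1-3 says: "On Days 8, 9, 10, and 11, PK samples will be taken at predose". A Day 12 predose sample is also taken. On reporting, SAP 9.1 states that PSL concentrations "will be summarized by period, cohort, and nominal sampling times using descriptive statistics", with individual and geometric mean plots. Neither document gives a criterion for steady state or a consequence if it is not reached. SAP 4.2.1 places the non-compartmental analysis under a separate guideline whose content is not in the documents, so a rule there cannot be excluded.

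**The concern.** The profile sits at the lower edge of the time that the protocol itself calculates for Cohort B, and most of the 4-to-6-day range falls after the Day 12 dosing interval has ended. Healthy controls, at 2 to 3 days, should be at plateau. Any shortfall would then be one-sided: AUCτ and Cmax,ss would be too low in Cohort B, CLss/F too high, and the impaired-to-healthy ratio too close to 1. AUCτ and Cmax,ss are primary, and the ANOVA in SAP 9.1 compares them between cohorts, so the study could understate the effect it was set up to measure.

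The doubled terminal half-life of 12 h does not dispose of the worry, because Protocol 4.2 says that accumulation exceeded what single-dose kinetics predict. With no criterion written down, it also looks as if the steady-state label could be kept or dropped after the data are seen.

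**Working it through.** **The plan's own figure.** 2 × (2 to 3 days) = 4 to 6 days. It reproduces.

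**Timing.** Day 8 8:00am to Day 12 8:00am = 4 × 24 = 96 h = 4.0 days. The interval ends at 108 h = 4.5 days. Day 12 is inside the range, so the two sections do not contradict each other.

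**Which analyte sets the upper end.** By the usual five half-lives (a convention assumed here), the metabolite at the 28 h that Protocol 4.2 assumes needs 5 × 28 = 140 h = 5.8 days. The parent at 12 h needs 5 × 12 = 60 h = 2.5 days. The upper end of the range therefore fits the metabolite, whereas the primary endpoints are parent only.

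**Shortfall for the parent.** Assume linear one-compartment accumulation and a dosing interval of 12 h. The share of plateau reached in the ninth interval is 1 − 2^(−108/t½), the same for AUCτ and Cmax,ss. To allow for the larger accumulation, obtain an effective half-life from the stated ratio R as t½ = 12 × ln 2 / (−ln(1 − 1/R)), and double it for Cohort B. For comparison, a 6 h half-life predicts R = 1/(1 − 2^(−12/6)) = 1.33. The last column is 2.0 × (Cohort B share / Cohort A share).

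| Basis | t½ A, h | t½ B, h | A share | B share | True 2.0 reads |
|---|---|---|---|---|---|
| Terminal half-life | 6.0 | 12.0 | 100.0% | 99.8% | 2.00 |
| R = 1.59 | 8.4 | 16.8 | 99.99% | 98.8% | 1.98 |
| R = 1.7 | 9.4 | 18.7 | 99.97% | 98.2% | 1.96 |
| R = 2.11 | 12.9 | 25.9 | 99.7% | 94.4% | 1.89 |

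**Scale.** With the CV of 40% and 12 per group in Protocol 9.8, the log-scale SD is √ln(1.16) = 0.385. The 90% CI half-width is t(0.95, 22) × 0.385 × √(2/12) = 1.717 × 0.157 = 0.270, a factor of 0.76 to 1.31. The log-scale bias is ln(2.0/1.964) = 0.018 at R = 1.7 and ln(2.0/1.895) = 0.054 at R = 2.11, which is 7% and 20% of that half-width. Power (noncentral t, one-sided 0.05) is 99.6% at a ratio of 2.0 and 98.9% at 1.89; the plan claims more than 90%.

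**Would a formal check help?** The like-for-like comparison uses morning predose samples, because the evening dose follows a different meal: participants "will complete a standard meal 30 minutes prior to the evening dose", and a light one before the morning dose. The expected Day 12/Day 11 ratio is (1 − 2^(−96/t½)) / (1 − 2^(−72/t½)), which for Cohort B is 1.03, 1.04 and 1.08 at R = 1.59, 1.7 and 2.11. The documents give no within-participant trough CV, so take 15%, 20% and 30% as assumptions, with s = √ln(1 + CV²), n = 12 and half-width t(0.95, 11) × √2 × s/√12.

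| Assumed trough CV | 90% CI factor | Chance that the CI lies above 1 (R = 1.59, 1.7, 2.11) |
|---|---|---|
| 15% | 0.90 to 1.12 | 13%, 16%, 33% |
| 20% | 0.86 to 1.16 | 11%, 13%, 23% |
| 30% | 0.81 to 1.24 | 8%, 10%, 15% |

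A test would usually miss the drift it is meant to find, and an interval that includes 1 would not show steady state.

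**The case for a change.** The strongest opposing case takes the 6-day end of the range at face value for the parent. If steady state at 6 days means 96.9%, 95% or 90% of plateau (assumed definitions), the ninth interval is at 92.6%, 89.4% or 82.2%, and a true 2.0 reads 1.85, 1.79 or 1.64 with Cohort A taken as complete. That would matter more. But those definitions imply half-lives of 28.8, 33.3 and 43.3 h in Cohort B. Halved for healthy people, they are 14.4, 16.7 and 21.7 h, and the same accumulation formula then gives R = 2.28, 2.54 and 3.14. All lie above the top of the stated range, 2.11, so the parent's own figures do not support this case.

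A second argument is that single-dose AUC cannot fully stand in for AUCτ, since accumulation exceeded the single-dose prediction. This stands in part. If kinetics are linear, single-dose AUC, which is also primary, targets the same cohort ratio without this bias. If they are not, the multiple-dose parameters carry information of their own, and the shortfalls above are only illustrative. Protocol 4.2 also describes biphasic disposition, which a one-compartment model simplifies.

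Third, the metabolite at 28 h would be at 1 − 2^(−108/28) = 93.1% of its plateau. That is a larger shortfall, but metabolite exposures are other endpoints, which SAP 9.3 summarises descriptively, and SAP 9.1 specifies the cohort ANOVA for PSL only.

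Finally, a written rule would limit choice after the fact. That is true only if it says how much rise counts, and the trough data are too imprecise to support a useful threshold.

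**Conclusion.** The observation is accurate: neither the protocol nor the SAP gives a steady-state criterion, and Day 12 is at the early end of the stated range. It does not call for a change. The timing agrees with Protocol 4.2. For padsevonil the likely understatement of the cohort ratio is 0.2% to about 2%, with 5% to 6% as an upper case that treats the top of an accumulation range as a cohort average. The single-dose primary endpoints are untouched, and the stated power still holds.

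The missing detail is one that analysts fill sensibly. The predose samples are scheduled, SAP 9.1 already summarises them by cohort and nominal time with geometric means and 95% CIs, and a rising Cohort B trough would prompt an ordinary caution in the study report that the parameters describe ninth-dose exposure. A formal test would alter no estimate and would usually be inconclusive.

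This rests on linear one-compartment accumulation, on the protocol's doubling assumption, and on assumed trough CVs of 15% to 30%. A much longer parent half-life in Cohort B than the protocol assumes would enlarge the shortfall.

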### 4.3 Justification for dose

The maximum tolerated dose (MTD) of PSL was identified as repeat dosing of 400mg twice daily (BID) in Phase 1 studies. In this study, the planned doses are well under the MTD, and

100mg BID is one of the dose levels currently being investigated in the 2 pivotal efficacy studies (EP0091 and EP0092). Padsevonil is predominantly cleared hepatically; therefore, an increase of exposure of PSL is expected in these hepatically impaired participants. A dose of 100mg BID was selected to allow collection of PK and tolerability data in vulnerable participants who may have less tolerance to PSL as compared with healthy participants. In addition, selection of a dose level of 100mg BID, which is 4-fold lower than the MTD, provides an opportunity to characterize the effect of liver disease on PSL PK without exploring PSL exposure beyond the one achieved at the MTD.

#### **4.4 End of study definition**

A participant is considered to have completed the study if he/she has completed all periods of the study including the last scheduled procedure shown in the EOS Visit in the Schedule of Activities (Table 1-3).

The end of the study is defined as the date of the last scheduled procedure shown in the Schedule of Activities for the last participant in the study globally.

### **5 STUDY POPULATION**

Prospective approval of protocol deviations to recruitment and enrollment criteria, also known as protocol waivers or exemptions, is not permitted.

#### **5.1 Inclusion criteria**

Participants are eligible to be included in the study only if all of the following criteria apply at Screening and at Baseline (Day -1):

##### **Inclusion criteria for ALL study participants**

1. Participant must be male or female 18 to 70 years of age, inclusive, at the time of signing the informed consent.
2. Participant must have body weight of at least 50kg (males) or 45kg (females) and body mass index within the range 18 to 38kg/m^2 (inclusive).
3. Participant must be capable of giving signed informed consent as described in Appendix 1 (Section 10.1), which includes compliance with the requirements and restrictions listed in the informed consent form (ICF) and in this protocol.
4. Participant must be considered reliable and capable of adhering to the protocol, according to the judgment of the Investigator, and must be capable of communicating satisfactorily with the Investigator.
5. Participants must meet the following requirements to be included in the study:
  - A male participant must agree to use contraception as detailed in Appendix 4 (Section 10.4) of this protocol during both Treatment Periods and for at least 7 days after the last dose of study medication and refrain from donating sperm during this period.
  - A female participant is eligible to participate if she is not pregnant (see Appendix 4; Section 10.4), not breastfeeding, and at least 1 of the following conditions applies:
    - Not a woman of childbearing potential (WOCBP) as defined in Appendix 4 (Section 10.4)

OR

A WOCBP who agrees to follow the contraceptive guidance in Appendix 4 (Section 10.4) during both Treatment Periods and for at least 90 days (or 5 terminal half-lives) after the final dose of study medication.

### **Specific inclusion criteria for study participants WITHOUT hepatic insufficiency**

6. Participants must be healthy as determined by medical evaluation, including medical history, physical examination, laboratory tests, and cardiac monitoring.

Note: Participant has clinical laboratory test results within the local reference ranges or values that are considered not clinically relevant by the Investigator and approved by the UCB Study Physician. Laboratory parameters outside the reference ranges can be retested, and if the retest result is within the reference range or considered clinically not relevant, the study participant will be allowed in the study.

### **Specific inclusion criteria for study participants WITH moderate hepatic insufficiency**

7. Participant must have characteristics that will meet the clinical criteria usually found in participants with chronic hepatic insufficiency, as determined by medical history and physical examinations (eg, echography, scintigraphy, biopsy, or some specific laboratory values as evidence) conducted within 3 weeks prior to the start of the Single-Dose Treatment Period. The degree of severity of hepatic impairment will be determined according to the classification of Child-Pugh (a score from 7 to 9 for Class B-moderate classification).

## **5.2 Exclusion criteria**

Participants are excluded from the study if any of the following criteria apply at Screening or at Baseline (Day -1):

### **Exclusion criteria for ALL study participants**

1. Participant is, in the judgment of the Investigator, likely to be unreliable or noncompliant or uncooperative during the study.
2. Participant has any medical or psychiatric condition that, in the opinion of the Investigator, could jeopardize or compromise the study participant's ability to participate in this study, such as a history of schizophrenia, or other psychotic disorder, bipolar disorder, or severe unipolar depression. The presence of potential psychiatric exclusion criteria will be determined based on the psychiatric history collected at Screening Visit.
3. Participant has a known hypersensitivity to any components of the study medication as stated in this protocol. Participant has sensitivity to any of the study interventions, or components thereof, or drug or other allergy that, in the opinion of the Investigator or UCB Study Physician, contraindicates participation in the study.
4. Participant has a lifetime history of suicide attempt (including an [REDACTED]), or [REDACTED] as indicated by a positive response ("Yes") to either Question 4 or Question 5 of the "Screening/Baseline" version of the Columbia Suicide Severity Rating Scale (C-SSRS) at Screening or at Baseline (Day -1).

5. Participant has participated in another study of an investigational medicinal product (IMP) within the previous 1 month (or 5 half-lives, whichever is longer) prior to Screening, or is currently participating in another study of an IMP.
6. Participant has had lymphoma, leukemia, or any malignancy within the past 5 years, except for basal cell or squamous epithelial carcinomas of the skin that have been resected with no evidence of metastatic disease for 3 years.
7. Participant is unable to tolerate oral medication or has a history of gastrointestinal bypass surgery.
8. Participant has past or intended use of over-the-counter or prescription medication including herbal remedies and hepatic enzyme inhibitors within 2 weeks or 5 half-lives prior to dosing, particularly for participants with hepatic impairment where  $t_{1/2}$  may be prolonged. Specific medications listed in Section 6.5.1 may be allowed. Participant has used hepatic enzyme-inducing drugs (eg, glucocorticoids, phenobarbital, phenytoin, isoniazid, or rifampicin, etc.) within 2 months prior to dosing unless required to treat an AE. This does not include oral contraceptives not exceeding 30 $\mu$ g ethinyl estradiol or postmenopausal hormone replacement therapy (HRT) or implants, patches, or intrauterine devices (IUDs) /intrauterine systems (IUSs) delivering progesterone (for female study participants) or acetaminophen with a maximal dose of 2g/day or with a maximum of 10g over 15 days. In case of uncertainty, the UCB Study Physician should be consulted.
9. Participant has a history of chronic alcohol or drug abuse within the previous 12 months. Participant has a positive pre-study drug/alcohol screen (to include at minimum: amphetamines, barbiturates, cocaine, opiates, cannabinoids, and benzodiazepines). A participant with a positive finding on the drug screen may still be enrolled at the discretion of the Investigator if a plausible clinical explanation exists (eg, prior or concomitant medication use).
10. Participant has any clinically relevant ECG finding at the Screening Visit or at Baseline (Day -1). Participant has an abnormality in the 12-lead ECG that, in the opinion of the Investigator, increases the risks associated with participating in the study. In addition, any study participant with any of the following findings will be excluded: (a) QT interval corrected for heart rate using Bazett's formula (QTcB) or Fridericia's formula (QTcF) >450ms in 2 of 3 ECG recordings; (b) other conduction abnormalities (defined as PR interval  $\geq$ 220ms); (c) irregular rhythms other than sinus arrhythmia or occasional, rare supraventricular or rare ventricular ectopic beats. In case of an out-of-range result, 1 repeat will be allowed. If the result is out-of-range again, the study participant cannot be included.  
NOTE A: The QTcB or QTcF is either machine-read or manually over-read.  
NOTE B: The specific formula used to determine eligibility and discontinuation for an individual participant should be determined prior to initiation of the study. In other words, several different formulas cannot be used to calculate the QT interval corrected (QTc) for an individual participant and then the lowest QTc value used to include or discontinue the participant.
11. Participant has a history of unexplained syncope or a family history of sudden death due to long QT syndrome.

12. Participant has renal impairment as indicated by an estimated glomerular filtration rate (GFR) <60mL/min, calculated by using the Chronic Kidney Disease Epidemiology Collaboration (CKD-EPI) equation (Levey, 2009):

$$\text{GFR}_{\text{CKD-EPI}} = 141 \times \min(\text{Scr}/\kappa, 1)^\alpha \times \max(\text{Scr}/\kappa, 1)^{-1.209} \times 0.993^{\text{Age}} \times 1.018 \text{ [if female]} \\ \times 1.159 \text{ [if Black]}$$

Where Scr is serum creatinine in mg/dL,

$\kappa$  is 0.7 for females and 0.9 for males,

$\alpha$  is -0.329 for females and -0.411 for males,

min indicates the minimum of Scr/ $\kappa$  or 1,

and max indicates the maximum of Scr/ $\kappa$  or 1

13. Participant tests positive for human immunodeficiency virus-1/2 antibody (HIV-1/2Ab) at Screening or within 3 months prior to the first dose of study medication.
14. Participant has made a blood or plasma donation or has had a comparable blood loss (>450mL) within the last 30 days prior to Screening. Blood donation during the study is not permitted.
15. Participant has received blood or plasma derivatives within the 6 months preceding Screening.
16. Participant has a consumption of more than 600mg of caffeine/day (200mL of coffee contains approximately 100mg of caffeine, 200mL of black tea approximately 30mg, and 200mL of cola approximately 20mg).
17. Participant smokes more than 10 cigarettes per day (or equivalent) or has done so within 6 months prior to the Screening Visit.
18. Participant ingests grapefruit, passion fruit, or pawpaw (as beverage, fruit, or supplements) within 72h before each administration of study medication. If this is the case at the start of the study, study participants may be rescreened.
19. Female participant tests positive for pregnancy, plans to get pregnant during participation in the study, or is breastfeeding.
20. Participant has a diet that deviates notably from the “normal” amounts of protein, carbohydrate, and fat, as judged by the Investigator.
21. Participant has undergone sudden and/or extreme changes in exercise levels for 2 weeks prior to Screening Visit.

